4.6.1.2 Pharmacodynamics

Not applicable.

4.6.1.3 Population pharmacokinetics

PK model-based analyses may be described in a separate analysis plan and reported independently.

4.6.1.4 Immunogenicity

4.6.1.4.1 Definitions

4.6.1.4.1.1 ADAb sample status (positive, negative, missing)

The ADAb sample results will be provided as “Positive Screen” (PS) or “Negative Screen” (NS). For samples presenting ADAb levels that are PS, a further confirmatory assay will be performed, and the result will be reported as either “Positive Immunodepletion” (PI) or “Negative Immunodepletion” (NI).

The ADAb status for each sample will be derived as follows:

- Sample values that are either NS, or PS and NI and where the bimekizumab concentration is less than the validated ADAb assay drug tolerance limit ($200\mu\text{g/mL}$) will be defined as ADAb-negative. Since the bimekizumab concentration is not collected at the SFU visit, the ADAb status will be defined as ADAb-negative if the ADAb sample values are either NS, or PS and NI at the SFU visit.
- Sample values that are either NS, or PS and NI and where the bimekizumab concentration exceeded the validated ADAb assay drug tolerance limit will be defined as inconclusive. Since the bimekizumab concentration is not collected at the SFU visit, the ADAb status will be defined as ADAb-negative if the ADAb sample values are either NS, or PS and NI at the SFU visit.
- Sample values that are PS and PI will be defined as ADAb-positive (regardless of availability of a titer value).
- Missing or non-evaluable samples will be defined as missing.

The PI samples will be titrated and the ADA_b titer (reciprocal dilution factor including minimum required dilution) will be reported. The PI samples will also be analyzed in a neutralizing assay to evaluate the anti-bimekizumab antibody neutralized target binding of bimekizumab (IL-17AA or IL-17FF or both) in vitro.

4.6.1.4.1.2 Cumulative ADA_b status

The ADA_b status (positive, negative, or missing) will be considered in a cumulative manner at each time point.

A study participant will be counted positive from the first visit at which the study participant achieved a positive ADA_b sample result to the end of the treatment period, regardless of any missing/inconclusive or negative ADA_b sample result.

If a study participant has only negative ADA_b samples or only 1 missing/inconclusive sample with all negative ADA_b samples up to that time point, the study participant will be classified as negative. An exception remains for the Baseline Visit where only 1 sample could be available. If the sample is missing/inconclusive, then the sample will be classified as being negative for the cumulative ADA_b status.

Otherwise, the study participant will be classified in the missing ADA_b category.

4.6.1.4.1.3 Overall ADA_b status (Positive, Negative, Missing)

A participant's Overall ADA_b Status will be derived for the following periods:

- Overall ADA_b Status in the Initial and Maintenance Treatment Period (combined): Including any visit during the Initial and Maintenance Treatment Period (as defined in Section 4.1.1.2). Thus, this summary will exclude data obtained at the SFU visit and will include data obtained at Baseline. This summary will display the overall ADA_b status up to Weeks 16 and 32 by treatment group (Placebo/BKZ 320mg Q4W, BKZ 320mg Q4W/Q8W).

For each time period, the participant will be classified as:

- Positive if the study participant has at least one positive sample up to the time point of interest (regardless of having missing/inconclusive data).
- Negative if the study participant has all the samples negative or only one missing/inconclusive sample with negative ADA_b samples up to the timepoint of interest.
- Missing if the study participant has missed more than one ADA_b result (or have more than one inconclusive sample) and all other available ADA_b samples are negative up to the time point of interest.

4.6.1.4.1.4 ADA_b categories

In addition, the ADA_b status will be further classified according to the following ADA_b categories:

- **Pre ADA_b negative – treatment emergent ADA_b negative (Category 1):** Includes study participants who are negative at Baseline and antibody negative at all sampling points (including SFU); one post-Baseline missing/inconclusive sample is allowed for study participants with pre-ADA_b negative sample. This group also includes study participants

who have a missing/inconclusive pre-treatment sample (eg, either missing/inconclusive or insufficient volume) at Baseline with all post-Baseline samples as ADA_b negative.

- **Pre ADA_b negative – treatment emergent ADA_b positive (Category 2):** Includes study participants who are ADA_b negative at Baseline and ADA_b positive at any sampling point post treatment (including SFU). This group also includes study participants who have a missing pre-treatment sample (either missing or insufficient volume) at Baseline with one or more ADA_b positive post-treatment samples.
- **Pre ADA_b positive – treatment emergent reduced ADA_b (Category 3):** Includes study participants who are ADA_b positive at Baseline, and ADA_b negative at all sampling points post treatment (including SFU).
- **Pre ADA_b positive – treatment emergent unaffected ADA_b positive (Category 4):** Includes study participants who are positive at Baseline and are positive at any sampling point post treatment (including SFU) and all post-Baseline samples have titer values <2.07 times the Baseline titer (where 2.07 is Minimum Significant Ratio [MSR]).
- **Pre ADA_b positive – treatment boosted ADA_b positive (Category 5):** Includes study participants who are positive at Baseline and have at least one post-treatment sample (including SFU) that has titer value ≥ 2.07 times the Baseline titer (where 2.07 is MSR).

Note: For any study participant who is positive at Baseline and positive at a post-Baseline time point, but for whom titers are not available to determine treatment unaffected or treatment boosted status, the study participant will be considered as treatment boosted (ie, Category 5), assuming no other samples are available.
- **Inconclusive (Category 6):** Includes study participants who have a positive pre-treatment sample and some post-treatment samples are missing/inconclusive, while other post-treatment samples are ADA_b negative.
- **Total treatment-emergent (Category 7 [Categories 2 and 5 combined]):** Includes study participants who are pre ADA_b negative – treatment emergent ADA_b positive (Category 2) and pre ADA_b positive – treatment boosted ADA_b positive (Category 5).
- **Total prevalence of pre-ADA_b positivity (Category 8 [Categories 3, 4, 5, and 6 combined]):** Study participants that are tested ADA_b positive at Baseline.
- **Missing (Category 9):** Includes study participants who have a negative or missing/inconclusive pre-treatment sample at Baseline and more than one post-treatment samples that are missing/inconclusive, while other samples are ADA_b negative. Also includes study participants who have a missing/inconclusive pre-treatment sample at Baseline, and only one missing post-Baseline sample with no ADA_b-positive.

4.6.1.4.1.5 ADA_b status groups for efficacy endpoint summaries

For the efficacy endpoint by ADA_b summaries (described below), the following ADA_b-efficacy status groups are defined:

- **ADA_b-positive** - Defined as study participants having at least 2 ADA_b-positive samples up to the time point of interest (ie, excluding Baseline, excluding SFU) regardless of other ADA_b-negative samples and/or missing or inconclusive samples

- ADAb-negative - Defined as study participants for whom either
 1. all samples to the time point of interest are ADAb-negative and there are no missing or inconclusive samples,
 2. only one sample is ADAb-positive and all other to the time point of interest (including Baseline) are ADAb-negative or missing/inconclusive, or
 3. only one sample is missing/inconclusive and the remaining ADAb samples are negative.
- Missing - Defined as study participants who do not fulfil the criteria for one of the 2 groups listed above.

The ADAb data from Baseline up to the time point of interest will be used to derive the ADAb-efficacy status groups.

The rationale for requiring at least 2 time points in which the participant is confirmed positive is to exclude individuals who have only one occurrence of ADAb levels during the period of interest. Including such study participants would increase the number of ADAb-positive participants with potentially no impact on efficacy.

4.6.1.4.1.6 Neutralizing anti-bimekizumab antibodies (NAb) categories

The NAb will be assessed using IL-17AA- and IL-17FF- specific assay methods, respectively. A NAb result will be positive or negative to each specific NAb assay or both.

Any NAb results derived from samples with drug concentrations higher than the drug tolerance limits of the NAb assays (100µg/mL) will be labeled 'inconclusive'. All inconclusive results will be regarded as missing.

Study participants will be assigned an overall NAb classification, inclusive of Baseline and post-Baseline results from NAb assay:

- NAb negative:
 - ADAb positive / NAb negative: No NAb positive samples for IL-17AA and IL-17FF at Baseline or post-Baseline. This group also includes study participants who have only one missing sample and all other available samples during the period of interest are negative.
 - ADAb negative: negative samples (refer to Section 4.6.1.4.1.3) are not analyzed for NAb.
- NAb positive: One or more positive samples (IL-17AA positive, IL-17FF positive, or both) at Baseline or post-Baseline (regardless of missing samples). Study participants who are NAb positive will be further classified as follows:
 - Positive for IL-17AA only: one or more positive samples for IL-17AA at Baseline or post-Baseline (and no samples are positive for IL-17FF).
 - Positive for IL-17FF only: one or more positive samples for IL-17 FF at Baseline or post-Baseline (and no samples are positive for IL-17AA).
 - Positive for both IL-17AA and IL-17FF: one or more positive samples for both IL-17AA and IL-17FF at Baseline or post-Baseline.

- NAb Missing: more than one relevant NAb samples are missing/inconclusive and other available NAb samples during the period of interest are negative, eg, missing or insufficient sample left for NAb testing.

4.6.1.4.1.7 ADAb Sample Inclusion and Exclusion Rules

The following rules will be implemented for by-visit ADAb summaries if applicable:

- If the ADAb sample is collected within ± 14 days (excluding the Week 32, PEOT, or SFU visit) relative to the visit date at which the IMP was administered, the ADAb result for that sample will be associated with the scheduled visit and summarized accordingly.
- In all cases, this will include unscheduled assessments (if a dose was administered at an unscheduled visit).

Samples collected outside the relevant windows described above will be excluded from the ADAb by-visit summaries and will be listed only.

For samples associated with the Week 32, PEOT, or SFU, all ADAb data obtained will be included in the by-visit summaries.

All other summaries of ADAb (as described in the following sections) will use all available (both scheduled and unscheduled) data.

The reason for exclusion will be assigned as one or more of the following:

- Sample collected out of window relative to current dose (or visit)
- More than one sample obtained at the same visit

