3 POPULATIONS FOR ANALYSIS

The Enrolled Set (ES) will consist of all study participants who have given informed consent.

The Randomized Set (RS) will consist of all randomized study participants.

The Safety Set (SS) will consist of all study participants who receive ≥ 1 dose of IMP (bimekizumab or placebo).

The Full Analysis Set (FAS) will consist of all randomized study participants who receive ≥ 1 dose of IMP and have a valid measurement for each of the co-primary efficacy endpoints at Baseline.

The Active Medication Set (AMS) will consist of all study participants who receive ≥ 1 dose of active IMP (bimekizumab).

The Maintenance Set (MS) will consist of all study participants who receive ≥ 1 dose of active IMP (bimekizumab) in the Maintenance Treatment Period.

The Per-Protocol Set (PPS) will consist of all study participants in the RS who have no important protocol deviations affecting the co-primary efficacy endpoints. Important protocol deviations

will be predefined, and study participants with important protocol deviations will be evaluated during ongoing data cleaning meetings prior to database lock. The classification of PPS will be determined at blinded data evaluation meeting before unblinding of the data. The classification of study participants with important protocol deviations related to treatment group information will be re-determined after general unblinding.

The Pharmacokinetics Per-Protocol Set (PK-PPS) will consist of all randomized study participants who receive ≥ 1 dose of active IMP (bimekizumab) and provide ≥ 1 quantifiable plasma concentration post dose without important protocol deviations that would affect the concentration.

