4.1.2 Definition of baseline values

A Baseline value for a study participant is defined as the latest measurement for that study participant up to and including the day of first IMP administration, unless otherwise stated. If a Baseline assessment is taken on the same day as first IMP administration, it is eligible to be used as the Baseline value, even in the case that the time of the assessment is recorded as taking place after the time of first IMP administration. This is considered acceptable as this measurement is still the best representation of the Baseline value of the given assessment since it is highly unlikely that the IMP could have an impact on any measurement in such a short period of time. However, such cases should be rare as study center personnel are instructed to do all assessments at the Baseline visit prior to administering IMP. One exception to this rule is plasma concentration. If Baseline plasma concentration is measured at a time after the first IMP administration, then it should not be eligible to be considered as a Baseline plasma concentration. Such cases should be discussed with the quantitative clinical pharmacologist. If a Baseline measurement is missing or not collected, and a Screening value is available, the Screening value will be utilized as Baseline instead.

Baseline values for component scores should be computed using components from the same visit where the relevant measurements were recorded prior to dosing. For example, if the component scores on the Baseline visit cannot be derived due to missing components, the Baseline value for the component score should be calculated using the Screening visit values if the Screening visit has all of the components.

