- A summary of the number and percentage of study participants with a given CTCAE grade (0,1,2,3, or 4) based on minimum/maximum post-baseline value by laboratory variable and treatment group. Two separate tables will show results for the ITP (for the SS) and the initial and maintenance treatment period (combined) (for the AMS).
- Shift tables of the number and percentage of study participants experiencing CTCAE grade 0,1,2,3, or 4 values (as applicable) at Baseline to minimum/maximum post-Baseline CTCAE grade, by laboratory variable and treatment group. Two separate tables will show results for the ITP (for the SS) and the initial and maintenance treatment period (combined) (for the AMS).
- By-study participant listings of all laboratory data (including urinalysis) will be provided. These listings will be presented by treatment group and will include: center, study participant identifier, age, sex, race, weight, visit, laboratory variable, result (with abnormal values flagged as “L” or “H” accordingly) and unit.
- A separate listing will be provided for laboratory results classified as Grade 3 or Grade 4 for the SS.

The table for markedly abnormal liver function tests (LFTs) will contain data beyond the CTCAE Grade 3 thresholds outlined in Section 6.10.1 in order to allow for a more thorough review of elevated LFTs. There will be one table which will list the count and percentage of study participants meeting the below criteria at any time during the study:

- AST: >3xUpper Limit of Normal (ULN), >5xULN, >8xULN, >10xULN, >20xULN
- ALT: >3xULN, >5xULN, >8xULN, >10xULN, >20xULN

- AST or ALT: >3xULN, >5xULN, >8xULN, >10xULN, >20xULN
- Bilirubin: >1.5xULN, >2xULN
- ALP: >1.5xULN

For any participant with at least one markedly abnormal LFT (AST >3xULN, ALT >3xULN, bilirubin >3xULN, or ALP >1.5xULN) the New Ratio (nR) will be calculated as the ratio of either maximum ALT or maximum AST (whichever is higher) to ALP, all expressed as multiples of their ULN as follows:

- $nR = [\text{maximum}(\text{ALT/ULN or AST/ULN})]/(\text{ALP/ULN})$

A plot displaying shift in liver function tests from baseline to maximum post-baseline result and a plot showing maximum post-baseline Total Bilirubin versus maximum post-baseline AST and ALT will be provided for the AMS if there are study participants with reported markedly abnormal LFT.

The following definition of potential drug induced liver injuries (pDILI) will be used (all criteria must be met at the same assessment):

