4.6 Other analyses

4.6.1 Other endpoints and/or parameters

4.6.1.1 Pharmacokinetics

PK variables will be analyzed for all study participants in the PK-PPS. Bimekizumab plasma concentrations will be summarized for each treatment group at each scheduled visit. All plasma concentration data will be reported in µg/mL in the tables, figures, and listings. For study participants randomized to placebo and switched to BKZ 320mg Q4W, the baseline corresponds to the Week 16 pre-dose observation.

PK summaries will be based on observed values. No imputation will be used. However, if plasma concentration measurements are below limit of quantification (BLQ), then for calculation of the derived statistics the result will be set to 0.125 µg/ml, which is ½ of the lower limit of

quantification (LLOQ). Descriptive statistics including number of values, geometric mean, geometric coefficient of variation, geometric mean 95% CI, mean, SD, median, minimum, and maximum if applicable will be calculated if at least $\frac{2}{3}$ of the values of interest are above the LLOQ and $n \geq 3$. Otherwise, only number of values, median, minimum, and maximum will be presented.

If the dosing for a visit is ± 21 days out of window, then the plasma concentration from that visit and all subsequent visits will be excluded from the PK summary.

If the PK sampling date is >1 day after the dosing date, data points will be excluded from the PK summary tables and figures, but not from the listing.

However, all PK concentrations will be listed for the AMS.

If more than 10% of the PK concentration results have been excluded from the table summaries, the PK excluded results will be listed in a separate listing.

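### Placebo participants who switch at Week 16 keep a Day 1 antibody baseline, so a positive result or titer rise on placebo is classed as treatment-emergent (ADAb Categories 2, 5 and 7)

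*SAP*

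**What the plan says.** - **Baseline.** SAP 4.1.2 defines it as the "latest measurement for that study participant up to and including the day of first IMP administration, unless otherwise stated". SAP section 3 shows that IMP covers both treatments: the Safety Set is those who "receive ≥ 1 dose of IMP (bimekizumab or placebo"). A placebo participant's Baseline is therefore Day 1.
- **Antibody categories.** In SAP 4.6.1.4.1.4, Category 2 is negative at Baseline and then "positive at any sampling point post treatment (including SFU). This group also includes study participants who have a missing pre-treatment sample". Category 5 is positive at Baseline with a later titer at least 2.07 times the Baseline titer. The two feed "Total treatment-emergent (Category 7 [Categories 2 and 5 combined"]). None of these rules requires the later sample to follow bimekizumab.
- **Data used.** SAP 4.6.1.4.2.1 runs the antibody tables on the Active Medication Set, which includes placebo participants once they have received bimekizumab. SAP 4.6.1.4.1.7 uses every available sample outside the by-visit tables.
- **PK.** For participants switched from placebo to bimekizumab, SAP 4.6.1.1 states that "the baseline corresponds to the Week 16 pre-dose observation". SAP 4.6.1.4 has no matching sentence.
- **Overall ADAb status.** SAP 4.6.1.4.1.3 reports it up to Weeks 16 and 32, with a Placebo/BKZ Q4W column, and adds: "Thus, this summary will exclude data obtained at the SFU visit and will include data obtained at Baseline".
- **Laboratory data.** SAP 4.5.3.1 plans "Shift tables of the number and percentage of study participants experiencing CTCAE grade 0,1,2,3, or 4 values (as applicable) at Baseline" against the worst post-Baseline grade, with one version on the Active Medication Set.

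**The concern.** A treatment-emergent antibody rate should count antibodies that appear or rise after exposure to the drug. In the placebo arm, exposure starts at Week 16, while the clock for the categories starts at Day 1. Any confirmed positive in between reflects assay background or antibody unrelated to bimekizumab, yet it would be reported as treatment-emergent to bimekizumab. The table of first Category 7 occurrence by visit could even show such cases at Weeks 8 and 16.

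The column holds about 30 people, so a single case is visible. The SAP already accepts the principle for PK, and antibody results are read alongside PK, so the two sections would work from different baselines for the same people.

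**Working it through.** The documents state no antibody rate, so there is no plan figure to reproduce. The check applies the SAP's rules to the sampling schedule and then scales the result.

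**1. Which samples precede bimekizumab in the placebo arm?** The antibody row of the protocol's Schedule of Activities (Table 1-1) marks Baseline and Weeks 8, 16, 24, 32/PEOT and SFU. A note to that table puts all assessments before dosing. Protocol Table 6-2 gives this arm its first bimekizumab at Week 16. So two of the five post-Baseline samples (Weeks 8 and 16) are drug-naive.

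**2. What do the rules do with them?**

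| Result on placebo | Class as written | Class with a Week 16 pre-dose baseline |
|---|---|---|
| Day 1 negative, Week 8 positive, Week 16 negative | Category 2, hence 7 | Decided by Weeks 24, 32 and SFU only |
| Day 1 negative, Week 16 positive | Category 2, hence 7 | Positive at baseline: Category 3, 4, 5 or 6 by later samples |
| Day 1 positive, titer at least 2.07 times Day 1 at Week 8 or 16 | Category 5, hence 7 | Set by the Week 16 status and titer, compared with later samples |

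A missing Day 1 sample followed by a placebo-period positive also goes to Category 2 as written.

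**3. Size per case.** 120 participants at 3:1 gives 120 × 1/4 = 30 on placebo. One case moves the Placebo/BKZ Q4W column by 1/30 = 3.3 percentage points, or 1/120 = 0.8 points over both groups together.

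**4. How many cases?** Let p be the chance of a confirmed positive per drug-naive sample. It is assumed. Take all 30 as negative on Day 1 and all as switching. With independent samples, the chance of at least one positive in two is P = 1 − (1 − p)², the expected count is 30P, and the chance of at least one case is 1 − (1 − P)³⁰. If the two samples always agree, the expected count is 30p.

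| Assumed p | P | 30P (independent) | At least one case (independent) | 30p (fully correlated) |
|---|---|---|---|---|
| 1% | 1.99% | 0.60 | 45% | 0.3 |
| 2% | 3.96% | 1.19 | 70% | 0.6 |
| 5% | 9.75% | 2.93 | 95% | 1.5 |

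**5. Gross versus net.** Some of these participants would become treatment-emergent after the switch anyway. If that share is assumed to be 10–50%, the independent range falls to between 0.60 × 0.5 = 0.3 and 2.93 × 0.9 = 2.6. Category 5 cases are not included in any of these counts.

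**6. Laboratory shift tables.** SAP 4.1.4 admits only post-switch data for switchers in the BKZ 320mg Q4W column. SAP 4.5.3.1 assigns results by sampling date and time at risk, and SAP 4.5.1.3 starts the switchers' time at risk with the Maintenance Treatment Period. An abnormality that came and went on placebo is therefore already excluded. What remains is one that arose on placebo and persists past the switch: it is compared with Day 1 and appears as a shift under bimekizumab.

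**The case against.** The best defence is that the term for post-treatment in Category 2 is undefined and, in tables built on the Active Medication Set, might mean after bimekizumab. The text does not support that. The same definitions equate the pre-treatment sample with Baseline, and Baseline is set by first IMP. The post-switch restriction in SAP 4.1.4 does not help either: it governs a safety-table column and does not move Baseline, so an antibody first seen on placebo and still present later would remain treatment-emergent.

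Other objections stand and limit the point. A reader might infer each of the following, and the documents do not bear it out:

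- *That overall ADAb status up to Week 32 is also wrong.* It is a prevalence measure that includes Baseline by design and is not labelled treatment-emergent.
- *That all PK, efficacy and AE summaries by antibody status inherit the error.* The PK tables use cumulative or NAb status, which count Baseline positives too; they are affected only so far as they use placebo-period positives. In the AE split, Categories 2 to 6 all contribute after the first positive, so a Week 16 positive stays in the same column after a reset and only a Week 8-only positive changes. The efficacy groups need two positive samples. Two placebo positives under independence have probability p² = 0.01–0.25%, under 0.1 of 30, although one placebo positive plus one later positive could still qualify by Week 32.
- *That assay background inflates only one column.* Both groups have five scheduled post-Baseline samples, so background reaches both. What is specific to the switchers is that two of their five precede the drug.
- *That placebo-period results are hidden.* By-visit status, first occurrence by visit, participant listings and overall status up to Week 16 already show them.

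**Conclusion.** The gap is real for Categories 2, 5 and 7 in placebo participants who switch. Followed as written, the SAP counts a positive or a titer rise that predates any bimekizumab as treatment-emergent, while its PK section already uses the right baseline for the same people.

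The certain part is the 3.3 points per case. The number of cases rests on a drug-naive positivity rate that is absent from the documents and on how far the Week 8 and Week 16 results agree. The counts of 0.6–2.9 and 0.3–1.5 of 30 illustrate an assumed 1–5% and are gross figures. The laboratory issue is confined to placebo-period abnormalities that persist past the switch.

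Antibody level is a tertiary endpoint reported descriptively. No co-primary or key secondary test is touched, and the BKZ Q4W/Q8W column of 90 participants is correct as planned.

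**What to change.** In SAP 4.6.1.4.1.4, state that for Placebo/BKZ Q4W participants the ADAb baseline for Categories 1–9 and for the titer ratio is the Week 16 pre-dose sample or, if that is missing, the last sample before first bimekizumab. Only later samples then count as post-treatment. Use the same time origin for first Category 7 occurrence by visit and for the AE split at the first ADAb-positive result.

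Leave overall ADAb status as a prevalence measure. No new display of placebo-period results is needed, since the by-visit tables already give Weeks 8 and 16.

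For the laboratory shift tables on the Active Medication Set, use the switchers' last value before bimekizumab as baseline.

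The cost is SAP wording and a re-derived baseline flag, with no new samples. The drawback is comparability: switchers would have three scheduled post-baseline antibody samples (Weeks 24, 32 and SFU) against five in the other group, so they have fewer chances to be found positive. A table footnote should say so.

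### Two separate faults in the ADAb status rule for the efficacy summaries: some fully observed participants are classed Missing, and some whose only result is positive are classed ADAb-negative

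*SAP*

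**What the plan says.** SAP 4.6.1.4.1.5 defines three ADAb groups for the efficacy summaries.

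- **ADAb-positive** requires at least two positive "samples up to the time point of interest (ie, excluding Baseline, excluding SFU) regardless of other" results.
- **ADAb-negative** can be reached by three routes. Limb 1: every result is negative "and there are no missing or inconclusive samples". Limb 2: exactly one sample is positive "and all other to the time point of interest (including Baseline) are" negative, missing or inconclusive. Limb 3: "only one sample is missing/inconclusive and the remaining" results are negative.
- **Missing** is whatever is left: "Defined as study participants who do not fulfil the criteria for one of the 2 groups listed above".

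The section then states that ADAb "data from Baseline up to the time point of interest will be used to derive the" groups. It gives the reason for asking for two positives as "to exclude individuals who have only one occurrence" of antibodies in the period of interest.

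These groups serve the PASI90 and IGA 0/1 responder summaries by ADAb status at Weeks 16 and 32 (SAP 4.6.1.4.2.3). They also serve the status table for the efficacy subgroup analysis (SAP 4.6.1.4.2.1). That section drops the missing group from display when at least 95% of participants are in the other groups.

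**The concern.** The positive rule and limb 2 of the negative rule count different samples. A participant can have too few positives for one and too many for the other, and then falls into Missing even though every sample was obtained and gave a clear result. Limbs 2 and 3 also treat missing samples differently, so a participant with a positive result can be called antibody-negative more easily than one with a negative result.

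At stake is the descriptive comparison of response with and without antibodies. Some antibody-positive histories drop out of the comparison, and some participants whose only known result is positive join the negative group. The first group conflicts with the SAP's other classifications. Under SAP 4.6.1.4.1.4 these participants are in Category 4 or 5, and Category 5 counts towards total treatment-emergent ADAb. Under SAP 4.6.1.4.1.3 their overall status is positive, because Missing there requires more than one missing or inconclusive result and no positive one. The same person could be treatment-emergent positive in one table and Missing in another.

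**Working it through.** The plan gives no figure to reproduce, so the check applies the rules as written to every possible record.

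**Inputs.** ADAb is sampled at Baseline and Weeks 8, 16, 24 and 32, then at SFU (Protocol Table 1-1, read from column positions). Up to Week 16 a participant has 3 scheduled samples including Baseline; up to Week 32, 5. Write P for positive, N for negative and M for missing or inconclusive, with Baseline first.

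**Fault 1: complete records.** A complete record is Missing if it has fewer than two positives after Baseline but two or more including Baseline. That means Baseline positive and exactly one later positive.

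- Week 16: 2³ = 8 complete patterns. Two are Missing (PPN, PNP), 2 are ADAb-positive and 4 ADAb-negative.
- Week 32: 2⁵ = 32 complete patterns. Four are Missing (PPNNN, PNPNN, PNNPN, PNNNP), 22 are ADAb-positive and 6 ADAb-negative.

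**Fault 2: records with missing samples.** Compare records that differ in one result.

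| Week 16 record | Class | N replaced by P | Class |
|---|---|---|---|
| NMM | Missing | PMM | ADAb-negative |
| MNM | Missing | MPM | ADAb-negative |
| MMN | Missing | MMP | ADAb-negative |

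The left-hand records fail limb 3, which allows one missing sample. The right-hand records pass limb 2, which has no limit. Up to Week 32 the reversal starts from records with no positive, at least two M and at least one N:

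- two M: 10 patterns with 3 N each, 30 changes
- three M: 10 patterns with 2 N each, 20 changes
- four M: 5 patterns with 1 N each, 5 changes

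In all, 25 starting patterns and 55 changes.

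**Are the two faults linked?** The same enumeration under each repair gives the following.

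| Rule | Complete records in Missing (Wk 16 / Wk 32) | Missing-to-negative changes (Wk 16 / Wk 32) |
|---|---|---|
| As written | 2 / 4 | 3 / 55 |
| Baseline counted in both | 0 / 0 | 3 / 55 |
| Baseline left out of both | 0 / 0 | 0 / 48 |
| Baseline in both, limb 2 capped at one missing | 0 / 0 | 0 / 0 |
| Baseline out of both, limb 2 capped at one missing | 0 / 0 | 0 / 0 |

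Aligning Baseline cures the first fault only. The second needs the cap.

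**Display rule.** If the 95% test is applied within a group of 90, 86/90 = 95.6% passes and 85/90 = 94.4% does not. Up to 4 participants classed Missing could then be absent from the status table. This is a ceiling, not an expected count.

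**The case against.** The strongest defence is that leaving Baseline out of the positive rule is deliberate, because antibody present before treatment need not bear on efficacy. The rationale refers to one occurrence within the period of interest. If that period is post-Baseline, PPN and PNP have a single occurrence, and the residual group could be read as indeterminate, with only its label at fault. Whether Baseline positivity should count is indeed the sponsor's choice. But the defence does not produce the class Missing. If Baseline is ignored, these records have one positive and belong with the other single positives in ADAb-negative. If it counts, they have two and belong in ADAb-positive.

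A reader might infer more than the documents support:

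- **That the closing sentence settles the matter.** It says Baseline data are used. It does not say that a Baseline positive counts towards the required two, and the negative rule's use of Baseline is enough to satisfy it.
- **That every by-ADAb efficacy output is affected.** The titer-category summaries and the individual plots grouped by ADAb category do not use this status. The over-time summaries refer to overall ADAb status, which may be the SAP 4.6.1.4.1.3 definition.
- **That repeated positives generally leave the positive group.** Anyone with two positives after Baseline stays ADAb-positive.
- **That affected participants vanish.** The 95% rule is stated for the status table. Individual results are listed and the nine ADAb categories are tabulated.
- **That pattern fractions are participant fractions.** Patterns are not equally likely, and the documents give no ADAb rates.

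**Conclusion.** Both faults follow from the text as written, and they have different causes. The first comes from counting Baseline in one definition and not in the other: it misfiles 2 of 8 complete patterns at Week 16 and 4 of 32 at Week 32. The second comes from the missing cap in limb 2. It makes a participant whose only observed result is positive ADAb-negative, while one whose only observed result is negative is Missing.

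The reach is limited to the descriptive PASI90 and IGA 0/1 summaries that use this status and to the efficacy-subgroup status table. No hypothesis test depends on it. The number of participants affected cannot be estimated: that would need the rate of Baseline positivity, the pattern of later results and the rate of missing samples, none of which is given. The counts assume scheduled samples only, whereas SAP 4.6.1.4.1.7 also admits unscheduled samples outside the by-visit summaries. The point is worth correcting because the rule cannot deliver what it is for, and the correction is nearly free.

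**What to change.** In SAP 4.6.1.4.1.5, make two changes.

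1. Use one sample set in both definitions. Either include Baseline in the positive rule (SFU still excluded), or remove Baseline from the negative rules and align the closing sentence.
2. Replace the three ADAb-negative limbs with one rule: at most one positive and at most one missing or inconclusive sample, the rest negative. Two or more positives remain ADAb-positive, and everyone else is Missing.

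Either version leaves no complete record in Missing and removes the reversal at both time points. They differ in where Baseline-positive participants with one later positive go: ADAb-positive if Baseline counts, ADAb-negative if it does not. The sponsor should state which is meant. If Baseline is left out, only two samples remain by Week 16, and a record of one positive and one missing would still be ADAb-negative, as would one negative and one missing. The sponsor should confirm that this is acceptable.

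It would also help to say in SAP 4.6.1.4.2.3 which definition the over-time summaries use. The cost is a few phrases and one derivation, with no new data.
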